We recognize a patient may, as a result of this protocol, get two PSMA-targeted PET/CT exams within a short period of time. This will result in a small amount of additional radiation. However, without this scan and extra radiation, there could be a significant delay in access to cancer therapy, a therapy which may be life extending. It should be recognized that the PSMA-targeted radionuclide therapy the patient is planning to undergo results in a significantly higher radiation exposure than the additional PSMA-targeted PET/CT scan included in this trial.

We intend to make the 68Ga-PSMA-11 PET/CT imaging and interpretation of that imaging available in the electronic record for patients and their care team, so they can guide clinical care decisions.

We anticipate referrals for 68Ga-PSMA-11 PET/CT under this protocol to come from Urology, Medical Oncology, Radiation Oncology, and Radiology. We anticipate performing up to six 68Ga-PSMA-11 PET/CT scans per day. We anticipate this trial will run for up to 12 months. Therefore, the total population of patients we plan to scan with 68Ga-PSMA-11 PET/CT is not expected to exceed 250.

It is possible we may need to extend this trial and increase the enrollment depending on the timing of the anticipated resolution of the Medicare and Insurance limitations on coverage described above. Alternatively, when our ability to produce an FDA approved version of 68Ga-PSMA-11 allows us to convert our clinical practice away from 18F-PSMA-DCFPyL this protocol will no longer be needed. That practice conversion is currently under active development and is dependent in part on completion of construction of new PET radiochemistry facilities in Charlton North.

Given that production of 68Ga-PSMA-11 is limited at our site, we may need to modulate access to patients in part depending on radiotracer and scanner availability. We also have limitations in terms of access to PET/CT. Thus, we will perform the majority of, or all of these 68Ga-PSMA-11 PET/CT exams within the research facilities of the PET Imaging Resource on Charlton 6.

Primary Endpoint: Safety

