Measurement: Monitoring of patients for self-reported unexpected adverse reactions from the time of injection until the time they leave the care of the Division of Nuclear Medicine. If any adverse reactions are reported, the patient will be evaluated by a nurse and/or physician and will receive appropriate care. The PI or those designated by the PI will ascertain the severity of the adverse event and how likely the adverse reaction was associated with the injected 68Ga-PSMA-11.

To date we have seen no adverse reactions to IV administered 68Ga-PSMA-11 at Mayo Clinic in Rochester and we have administered over 400 doses.

68Ga-PSMA-11 Administration

The injected dose will be 185 MBq (5 mCi) (range 111-259 MBq; 3-7 mCi) of 68Ga-PSMA-11. PET imaging will begin 50-100 minutes after injection. A use of existing Central/PICC lines is considered acceptable for 68Ga-PSMA-11 administration.

We may repeat a 68Ga-PSMA-11 injection and PET/CT in either of the following circumstances:

- The patient had an unavoidable delay in care (such as a motor vehicle accident) and there is evidence or clinical concern that the patient's cancer significantly progressed or responded to therapy in a way that could affect management of his cancer.
- The patient still meets the criteria for enrollment in the study and 3 months of time or more has elapsed since the last 68Ga-PSMA-11 injection.

68Ga-PSMA-11 PET/CT protocol

The established 68Ga-PSMA-11 PET/CT imaging protocol will be followed. The scans will be performed on the Siemens VISION 600 PET/CT or GE DMI PET/CT on Charlton 6. The CT will be performed without IV or oral contrast and will follow standard clinical PET/CT protocol parameters. The exams will cover the orbits to thighs, unless otherwise specified by the Radiologist/Nuclear Medicine physician protociling the specific exam for a given patient.

Patient selection for enrollment

Inclusion Criteria. All the following criteria must be met.

- An adult male patient who...
 - o is actively under the care of a Medical Oncology, Radiation Oncology or Urology physician at Mayo Clinic.
 - o is deemed eligible (or potentially/likely eligible) for PSMA-targeted radionuclide therapy by a Nuclear Medicine Physician or Radiologist in the Nuclear Medicine therapy practice, or by the Prostate Theranostic Tumor Board (PTuB)
 - eligibility will be documented in the medical record by the clinical practice

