 - it is acceptable for the patient to be eligible for PSMA-targeted radionuclide therapy in all regards except for having completed a PSMA-targeted PET scan showing PSMA-positive prostate cancer
 - It is acceptable for a patient to be potentially eligible for therapy, but have a relative contraindication, such as a minor laboratory abnormality, and be on the list for discussion at the PTuB in the future
 - o has not received a 68Ga-PSMA-11 PET/CT or PET/MR, or for whom a repeat 68Ga-PSMA-11 PET/CT exam is needed per the clinical practice to ensure eligibility
 - o does not otherwise have access to a reimbursable clinical 68Ga-PSMA-11 PET scan
 - o An adult above the ages of 18

Exclusion criteria. Any of the following.

- A patient who is:

- unable to consent per Mayo guidelines
- unable to lay still, or otherwise successfully complete the imaging exam

Study procedures

Patients who meet all inclusion and no exclusion criteria will be invited to participate in the study. The study coordinator will set up an appointment with the subject to discuss the study, answer any relevant questions, and obtain informed consent. The study coordinator will schedule the 68Ga-PSMA-11 PET/CT scan. Patient's participation in the study will end once their imaging visit is complete. The 68Ga-PSMA-11 PET/CT scans will be clinically interpreted with the report and imaging available in the patient's medical record.

Radiation Dose Estimate for CT Component of PET/CT

The effective dose for a trunk CT (orbits to mid-thigh) is 6.3 mSv for males. The effective dose for a 7 mCi IV injection of 68Ga-PSMA-11 is 4.4mSv.

Adverse Event (AE) Monitoring and Reporting

The site principal investigator is responsible for reporting any/all serious adverse events to the IRB and IND sponsor as described within the protocol, regardless of attribution to study agent or treatment procedure.

The sponsor/sponsor-investigator is responsible for notifying FDA and all participating investigators in a written safety report of any suspected adverse reaction that is both serious and unexpected.

Definitions:

Adverse Event: Any untoward medical occurrence associated with the use of a drug in humans, whether or not considered drug related.

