Note: An adverse event (also referred to as an adverse experience) can be any unfavorable and unintended sign (e.g., an abnormal laboratory finding), symptom, or disease temporally associated with the use of a drug, without any judgment about causality. An adverse event can arise from any use of the drug (e.g., off-label use, use in combination with another drug) and from any route of administration, formulation, or dose, including an overdose.

Suspected Adverse Reaction: Any adverse event for which there is a reasonable possibility that the drug caused the adverse event.

Note: For purposes of IND safety reporting, “**reasonable possibility**” means there is evidence to suggest a causal relationship between the drug and the adverse event. A suspected adverse reaction implies a lesser degree of certainty about causality than adverse reaction, defined below.

Unexpected: An adverse event or suspected adverse reaction is considered “unexpected” if

- It is not listed in the investigator brochure or.
- Is not listed at the specificity or severity that has been observed; or,
- If an investigator brochure is not required or available, is not consistent with the risk information described in the general investigational plan (protocol) or elsewhere in the current IND application (as amended).

Serious (previously SAE): An adverse event or suspected adverse reaction is considered “serious” if, in the view of either the investigator or sponsor, it results in any of the following outcomes:

- Death,
- A life-threatening adverse event,
- Inpatient hospitalization or (Prolongation of existing hospitalization), or
- A persistent or significant incapacity or substantial disruption of the ability to conduct normal life functions, or a congenital anomaly/birth defect.

Note: Important medical events that may not result in death, be life-threatening, or require hospitalization may be considered serious when, based upon appropriate medical judgment, they may jeopardize the patient or subject and may require medical or surgical intervention to prevent one of the outcomes listed in this definition.

Life-Threatening: An adverse event or suspected adverse reaction is considered “life-threatening” if, in the view of either the investigator or sponsor, its occurrence places the patient or subject at immediate risk of death.

Note: It does not include an adverse event or suspected adverse reaction that, had it occurred in a more severe form, might have caused death.

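### The primary safety endpoint is measured by self-reported reactions, so, read literally, a reaction that staff notice but the patient does not report is not counted

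*Protocol*

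**What the plan says.** The protocol names one endpoint in the text available for this review: "Primary Endpoint: Safety". The Measurement paragraph beneath it defines what is monitored as "Monitoring of patients for self-reported unexpected adverse reactions from the time of injection", and the window runs "until the time they leave the care of the Division of Nuclear Medicine".

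Two further steps follow in that paragraph. The first is care: "If any adverse reactions are reported, the patient will be evaluated by a nurse and/or physician". The second is grading: "The PI or those designated by the PI will ascertain the severity of the adverse event", together with a judgement on how likely the injected tracer is to be the cause. Neither step gives staff a stated part in detecting events for the endpoint.

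The section Adverse Event (AE) Monitoring and Reporting is wider. Under Definitions, an adverse event is "Any untoward medical occurrence associated with the use of a drug in humans, whether or not considered drug related", and the accompanying note says that it "can be any unfavorable and unintended sign (e.g., an abnormal laboratory finding), symptom, or disease temporally associated with the use of a drug". The site principal investigator is responsible for "reporting any/all serious adverse events to the IRB and IND sponsor", whatever the attribution. The section on FDA reporting requirements repeats the investigator's duty toward the sponsor for related and unrelated serious events alike. None of these rules depends on who noticed the event.

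**The concern.** In the Measurement paragraph, self-report is a condition on the event. Under the definitions section, an event qualifies by its nature, whoever notices it. The protocol therefore describes two collections with different entry rules and does not say that one feeds the other.

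This matters for two kinds of event within the existing window. One is an observed sign that the patient has not noticed or mentioned, such as a rash. The other is a reaction in a patient who is unable to speak for himself at the time, for example through loss of consciousness. Both are adverse events by the protocol's definition, and the second may be serious. Neither is an endpoint event if the measurement is followed as written. If staff record such an event anyway, whether it counts toward the endpoint has to be decided after it has been seen.

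**Working it through.** The check is a comparison of texts. The protocol states no figure for this endpoint to reproduce: there is no expected rate, threshold or precision target.

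**Step 1: entry conditions side by side.**

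| Feature | Primary Endpoint, Measurement | Adverse event and serious event rules |
|---|---|---|
| Source of the report | The patient | No limit |
| What qualifies | Unexpected adverse reactions | Any untoward occurrence, including signs and laboratory findings |
| Staff role stated | Evaluate once a reaction is reported; grade severity and attribution | Report all serious events |
| Link to the other column | None stated | None stated |

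**Step 2: run events with onset in the window through both rules.** Each is assumed to be an unexpected reaction.

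| Event | Adverse event by definition? | Counted in the endpoint as written? | Covered by the serious-event duty? |
|---|---|---|---|
| Reported by the patient, not serious | Yes | Yes | No |
| Seen by staff, not reported by the patient, not serious | Yes | No | No |
| Seen by staff, not reported by the patient, serious | Yes | No | Yes |

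The second row is missing from both collections. The third row is missing only from the endpoint.

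**Step 3: does the care sentence repair this?** The sentence "If any adverse reactions are reported, the patient will be evaluated by a nurse and/or physician" is passive and names no reporter, so it could cover a report by staff. What it triggers, however, is evaluation and care. It does not restate what the endpoint measures, and the sentence before it, which does, keeps the self-report condition.

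**Step 4: direction and size.** Let *a* be the number of qualifying reactions reported by patients and *b* the number noticed by staff only. The endpoint as written counts *a*. A count without the source limit is *a* + *b*. The difference is (*a* + *b*) − *a* = *b*, and *b* ≥ 0, so the written count can be too low but never too high on this account. The protocol gives nothing from which *b* can be estimated. The experience of no adverse reactions in over 400 earlier doses suggests that all such numbers are small, but it does not separate *a* from *b*.

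**The case against.** The strongest reply is that the Measurement paragraph describes a method of surveillance and not an exclusion. It nowhere says that staff-observed reactions are not counted. The next sentence drops the self-report qualifier, the one after it speaks of the adverse event in general, and the account of earlier doses says that no reactions were seen, which is not the language of patient report. It is quite possible that staff would record what they notice. This stands as far as intent goes. It does not change what the measurement sentence says, and if staff reports were intended, the wording should say so.

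The second reply is that serious events are captured and reported in any case. This is correct, and it limits the point to what the endpoint counts. It does not cover observed signs that are not serious.

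A reader might also infer more than the documents support:

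- **That a missed event would always be on file with FDA.** The protocol requires the sponsor to notify FDA only of a suspected adverse reaction that is both serious and unexpected. An arbitrary serious event during the visit need not qualify.
- **That staff are present throughout, so every visible reaction would be seen.** Continuous presence is not stated.
- **That exact confidence limits show the bias.** Assume 250 patients, the planned ceiling, with one injection each. Then 0/250 has a two-sided 95% upper limit of 1 − 0.025^(1/250) = 1.46%, and 1/250 is 0.40% (0.01% to 2.21%). These figures show what none or one event looks like at that sample size. They do not say how many events would be missed, 0.40% lies inside the interval for zero events, and the protocol ties no decision to a threshold.
- **That every serious event in the window should be an endpoint event.** The endpoint names adverse reactions. Counting serious events regardless of cause would mix coincidental events with reactions.

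**Conclusion.** The point holds as a defect in what the primary endpoint counts. As written, the measurement leaves out reactions that staff notice but the patient does not report, although the protocol's own definitions would class them as adverse events. The effect falls chiefly on observed signs and on patients unable to report. It can only lower the count, which favours the tracer. Its size cannot be derived from the document.

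The conclusion rests on a literal reading of the measurement sentence and on the absence of any statement linking the adverse event section to the endpoint. It does not show a gap in the reporting of serious events. That safety is the only endpoint is taken from the text available, part of which was removed before review.

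A separate restriction remains: the word *unexpected* keeps listed reactions out of the endpoint, whoever notices them. The change below does not address that.

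**What to change.** In the Measurement paragraph, replace *self-reported* with *self-reported or staff-observed*, and state that staff-observed means anything noticed in the course of existing care, with no added surveillance. For each event, record the source (patient or staff) and the attribution, using the five categories the protocol already defines.

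Before reporting, reconcile the endpoint count with the serious-event log, restricted to events with onset between injection and departure. List serious events judged unlikely or unrelated separately, and do not count them as reactions. Reconciliation alone is not enough, because non-serious observed signs do not appear in that log. The wording change is what brings them in.

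The cost is a short protocol edit, a source field wherever events are recorded, and one comparison of two lists. Because the definition is confined to existing care, it asks for no new visit, procedure or observation period. The downside is that the reported count may be slightly less favourable.
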